Despite the promising results, its efficacy in patients with acute severe manifestations, including organ-threatening cardiomyopathy and gastrointestinal involvement, remains under investigation. Additionally, while the efficacy of mepolizumab in ANCA-negative EGPA has been suggested by some studies, the MIRRA trial did not show a significant association between efficacy and ANCA status.

From March 2023, Mepolizumab 300 mg administered subcutaneously every 4 weeks has been approved in Italy as adjunctive therapy for patients aged 6 years and older with relapsed/remitting or refractory eosinophilic granulomatosis with polyangiitis (EGPA).

In clinical practice, the role of the otorhinolaryngologist is crucial in assessing the evolution of symptoms and naso-sinus signs in patients with EGPA and concomitant severe and uncontrolled CRSwNP.

Studies conducted in clinical practice, or 'real-life' studies, represent a fundamental tool for assessing the effectiveness of a therapeutic treatment. Our study aims to be one of the first to investigate the efficacy on the sino-nasal region of Mepolizumab 300 mg administered subcutaneously every 4 weeks in a real-life setting, thus contributing to an improvement in knowledge on the use of this drug in the management of EGPA.

OBJECTIVES

The *primary objective* of this study is evaluating the reduction of dimension of nasal polyps measured with Nasal Polyp Endoscopic Score (NPS)

The *secondary objective* is to evaluate the improvement in nasal symptoms and quality of life in the patient measured through symptom questionnaires, the improvements in terms of smell dysfunction and symptomatology related to eosinophilic otitis media; evaluate the need of surgery or systemic corticosteroids.

ENDPOINTS

Primary endpoint

The primary endpoints will be the Improvement of NPS score (indicative of polyps score reduction) at 12 months after start of therapy.

Secondary endpoints

- Improvement of SNOT-22 score (indicative of an improvement in quality of life)
- Improvement of VAS score for nasal obstruction
- Improvement of Nasal Congestion Score (NCS)
- Improvement of VAS score for smell;
- Improvement of sniffin' sticks score;
- Evaluate adherence to drug therapy with Mepolizumab 300, any suspension of the same and reasons for discontinuing treatment (lack of efficacy, complications reported, safety profile);
- Assess how many patients require FESS surgery and/or systemic steroids for sino-nasal symptoms during treatment;

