Patients receiving Mepolizumab 300 are generally evaluated in normal clinical practice at baseline and 30 days after first administration for an early re-evaluation. Subsequently, follow-up is continued with clinical re-evaluation every 3 months in the first year of treatment. Due to this reason, all participating centers will be asked to retrieve the clinical data of the visits performed at 30 days since the beginning of therapy and at 3,6,9 and 12 months.

As well, all centers will be required to provide data about any discontinuation of Mepolizumab due to adverse effects, intolerance to the drug, or related to its inefficacy. We will finally record any sino-nasal surgical treatment during treatment.

Variables

Data from the baseline clinical evaluation and follow-up visits will include a complete sensitized medical history and radiological or laboratory data carried out as normal practice.

In depth, we will collect:

- Anthropometric characteristics (age, height, gender, body mass index);
- Clinical characteristics (occupational exposure to particulate, exposure to cigarette smoke, allergies and sensitization to various allergens, presence of comorbidities, need for hospitalization for asthma and/or access to the emergency room in recent years);
- Assessment of symptoms and quality of life through validated questionnaires such as SNOT-22, Total Nasal-Symptom Score-VAS and Nasal Congestion Score (NCS);
- Nasal endoscopic staging: Nasal Polyp Score (NPS);
- Radiological extension of the CRSwNP: Lund-MacKay Score (LMS);
- Laboratory data (differential count of peripheral leukocytes, neutrophils, lymphocytes, monocytes, eosinophils, basophils), determination of total and specific IgE;
- Type of inflammation gathered from the result of non-invasive tests such as nasal cytology;
- Medications regularly taken by the patient for CRSwNP, and for comorbidities

(asthma, allergic rhinitis, etc.);

- Surgical history and any surgical treatment carried out before and during Mepolizumab therapy;
- Adverse reactions reported during drug treatment.

Sample size calculation

Based on the most recent literature, retrieved from the findings of preliminary phase III studies on Mepolizumab in the treatment of severe CRSwNP, a significant reduction NPS and SNOT-22 was observed. We therefore expect in our real-life experience a significant mean decrease at 12 months. Hence, hypothesing to assess a similar small effect size [$d = (\mu_1 - \mu_2) / \sigma$].

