Considering NPS as a primary outcome a sample size of 52 patients achieves 80% power to reject the null hypothesis of zero effect size when the population effect size is 0.40 and the significance level (alpha) is 0.05. Anticipating a 20% drop-out rate, 65 patients should be enrolled to obtain the final sample size of 52 subjects. The sample size calculation was performed with a two-tailed Student's t test for paired data with PASS2025 statistical software v25.0.2.

Statistical Analysis.

The sample will be described in its clinical and demographic characteristics by descriptive statistics techniques. In depth, qualitative data will be expressed as absolute and relative percentage frequency, whilst quantitative variables by either mean and standard deviation (SD) or median and interquartile range (IQR), as appropriate. To verify the Gaussian distribution of quantitative variables, the Shapiro-Wilk test will be applied.

Fluctuations over time of NPS, NCS, VAS related to nasal obstruction, smell, sleeping disorders, rhinorrhea and craniofacial pain, nasal identification test by Sniffin' sticks, SNOT-22 questionnaire, will be assessed by repeated measurement analysis of variance or Friedman's nonparametric test, as appropriate. Correction for multiple pairwise comparisons will be performed by the Bonferroni test.

Fluctuations of the different parameters over time will be further represented by "violin plots" for quantitative variables or bar plots for qualitative/ordinal data, by using R packages "*ggpubr*", "*ggstatsplot*", "*ggplot2*", "*ggprism*" and "*ggsignif*", on both the overall sample and stratified for past surgery, asthma or ASA triad.

Potential predictors of clinical response at each time point will instead be assessed by univariable and multivariable logistic regression models with the "*rms*" R package. We will consider clinical and anamnestic variables and scores related to the immediately previous time-point (e.g., for 3-months model we will consider scores at 1-month visit).

Statistical significance will be set at a p-value <0.05 . Suggestive p values will be also reported ($0.05 \leq p < 0.10$). All analyses will be performed with R software version 4.2.0 (CRAN[®], R Core 2022, Wien, Austria).

SAFETY / REGULATORY MANAGEMENT OF ADVERSE EVENTS

Definitions for medicinal product(s)

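### Surgery is recorded only up to the end of mepolizumab treatment, so the count is likely to understate the 12-month need for surgery; an event count to 12 months should stand beside it.

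*Protocol*

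**What the plan says.** The secondary objective (Protocol, Objectives) is to "evaluate the need of surgery or systemic corticosteroids". It does not restrict this to time on drug.

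The endpoint that serves it (Secondary endpoints) is narrower: "Assess how many patients require FESS surgery and/or systemic steroids for sino-nasal symptoms during treatment".

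Data collection follows the endpoint. Procedures states "We will finally record any sino-nasal surgical treatment during treatment", and the Variables list asks for "Surgical history and any surgical treatment carried out before and during Mepolizumab therapy". Surgery is thus covered before therapy and during therapy, and no item covers the time after therapy stops.

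Three other statements bear on the point:

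- Centres must supply "data about any discontinuation of Mepolizumab due to adverse effects, intolerance to the drug, or related to its inefficacy" (Procedures). Discontinuation and its reasons also form a secondary endpoint of their own.
- Visits are retrieved "at 30 days since the beginning of therapy and at 3,6,9 and 12 months" (Procedures), a window that runs from the start of therapy.
- The only medication item is "Medications regularly taken by the patient for CRSwNP, and for comorbidities" (Variables). It has no on-treatment limit, but it does not name systemic steroid courses either.

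**The concern.** The enrolled patients have severe disease and have already failed systemic steroids or surgery (Inclusion criteria). Someone who stops mepolizumab because it does not work is plausibly more likely than others to be operated on, or to receive a steroid course, in the following months. Leaving the recording window is then related to the event being counted.

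For example, a patient who stops at month 4 for inefficacy and has FESS at month 6 contributes a discontinuation but no operation. A patient operated on at month 6 while still on drug contributes an operation. Both needed surgery within the year.

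What is at stake is the reading of one secondary endpoint: a reader who takes the on-treatment count as the answer to the stated objective would think the need for surgery smaller than it was. Because this is a rule about what centres are asked to report, a statistical analysis plan could not recover the missing operations later.

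**Working it through.** **The plan's own figure.** The protocol gives no expected rate for surgery or steroids. Its only calculation is the sample size for the nasal polyp score, stated to give "80% power to reject the null hypothesis of zero effect size when the population effect size is 0.40". A two-sided paired t test at alpha 0.05 with effect size 0.40 has power 79.99% at n = 51 and 80.8% at n = 52, so 52 is reproduced. Allowing for 20% drop-out, 52 / (1 − 0.20) = 65, also as stated. This supplies the 65 used below and otherwise has no bearing on the point.

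**Which periods are covered for surgery.**

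| Period | Objective | Endpoint | Surgery recorded (Procedures, Variables) |
|---|---|---|---|
| Before therapy | not relevant | no | yes |
| On mepolizumab | yes | yes | yes |
| After stopping, up to month 12 | not excluded | no | no |

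The last row is the gap. No other part of the protocol fills it.

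**Direction.** The denominator is not stated, so each option is taken in turn.

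- *All patients who started.* An operation after stopping adds 0 to the numerator, and the patient stays in the denominator. Against the 12-month proportion, the count can only be equal or too low.
- *Patients who stop are excluded or censored at stopping.* The result leans favourable if those who stop need surgery more often than those who continue. This is plausible for stopping due to inefficacy, but it is an assumption.

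**Size, by assumption only.** Take all starters as the denominator. Let s be the share who stop and q the share of those who then have a first FESS on study before month 12. The missed share is s × q, and the missed number is 65 × s × q. Neither s nor q is in the documents.

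| s (assumed) | Patients who stop | q = 10% | q = 30% | q = 50% |
|---|---|---|---|---|
| 10% | 6.5 | 1 point (0.65 patients) | 3 points (1.95) | 5 points (3.25) |
| 20% | 13 | 2 points (1.3) | 6 points (3.9) | 10 points (6.5) |
| 30% | 19.5 | 3 points (1.95) | 9 points (5.85) | 15 points (9.75) |

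The 20% row is not the protocol's drop-out rate in another form. That rate is attrition for the polyp score analysis and is not described as stopping for inefficacy.

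**Steroids.** The two surgery items do not concern steroids. The on-treatment limit for steroids rests on the endpoint wording alone, so that part is less firmly fixed.

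**The case against.** The strongest reply is that this is declared scope. The endpoint and both recording items agree with each other, and the number of patients who need FESS or steroids while on the drug is a legitimate question in a single-arm, real-life study. The count is too low only against a 12-month target that the protocol does not declare. Treatment failure is also visible elsewhere: a patient who stops for inefficacy appears in the discontinuation endpoint, which worsens as such patients accumulate. Surgery after stopping, moreover, reflects time off drug and any later therapy, so it cannot replace the on-treatment figure.

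Most of this stands. The on-treatment count should stay, and the passages do not contradict one another outright. Three things remain. The objective is wider than the endpoint, and the protocol does not say that the narrowing is intended. The discontinuation endpoint shows that treatment failed, not whether surgery followed. The 12-month window already exists for the visits and for the primary endpoint.

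It can also be said that the on-treatment period is undefined and might be read loosely as the first year after starting. That is possible, but the Variables item, which names mepolizumab therapy itself, makes the narrower reading the plain one.

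**Conclusion.** The point holds as an inexpensive improvement to a secondary endpoint. On the plain reading, surgery after stopping mepolizumab is not collected, and the on-treatment count taken alone is likely to understate the need for surgery over 12 months. This rests on two assumptions: that some patients stop before month 12, and that some of those who stop are then operated on. The range of 1 to 15 percentage points follows wholly from assumed rates and is not an estimate.

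A reader might infer more than the documents support:

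- *That the protocol classes such a patient as not needing surgery, with a cut-off at the last dose.* It states neither a denominator nor a last-dose rule.
- *That the reported rate would be wrong by some multiple.* Any such ratio depends on an assumed number of on-treatment operations.
- *That centres which stop early would look better than others.* No comparison between centres is planned.
- *That steroid use is subject to the same recording limit as surgery.* Only the endpoint wording limits it.

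The primary endpoint's definition and the sample size are not affected.

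**What to change.** In Secondary endpoints, Procedures and Variables, ask centres to record every sino-nasal operation and every systemic steroid course given for sino-nasal symptoms, each with its date, up to 12 months from the start of therapy whether or not mepolizumab has been stopped. Add the date of the last mepolizumab dose, which also settles what counts as on treatment.

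Report two figures side by side: the proportion with an event within 12 months among all patients who started, and the on-treatment count. State with the first that events after stopping also reflect time off drug and any later therapy. State how many patients who stopped have no information to month 12.

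The cost is a change of wording, a few fields on the case report form and some chasing of records for patients who stop. Data will stay incomplete for those lost to follow-up, and the reported rate may be less favourable. The sample size and the care of patients are untouched.

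### NPS measured after on-treatment sinus surgery enters the primary 12-month before-after analysis, so surgical polyp removal counts as improvement on mepolizumab

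*Protocol*

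**What the plan says.** - **Primary endpoint (Protocol, Endpoints):** "The primary endpoints will be the Improvement of NPS score (indicative of polyps score reduction) at 12 months after start of therapy". It carries no condition on other treatment of the polyps.
- **Secondary endpoints:** on-treatment rescue is foreseen and tallied: "Assess how many patients require FESS surgery and/or systemic steroids for sino-nasal symptoms during treatment".
- **Procedures:** "We will finally record any sino-nasal surgical treatment during treatment". Visits are at baseline, 30 days, and 3, 6, 9 and 12 months.
- **Variables:** the list includes "Surgical history and any surgical treatment carried out before and during Mepolizumab therapy". For drugs it names "Medications regularly taken by the patient for CRSwNP, and for comorbidities". Dated short courses of systemic steroids are not mentioned.
- **Statistical Analysis:** changes over time in NPS and the other scores "will be assessed by repeated measurement analysis of variance or" Friedman's test, with Bonferroni correction for pairwise comparisons. No exclusion, failure score, censoring, covariate or sensitivity analysis is given for values after surgery or steroids. The one mention of surgery concerns the plots, shown "on both the overall sample and stratified for past surgery, asthma or ASA triad", which is surgery before treatment and not during it.
- **Study design and Population:** observational; every patient receives mepolizumab and no comparison group is described.

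**The concern.** NPS grades polyp size on endoscopy, and FESS removes what NPS grades. Suppose mepolizumab fails and the patient is operated on at month 6. If the month-12 NPS is used as recorded, that patient can be among the largest improvements in the primary analysis, while being counted as a treatment failure in the secondary one. The same event then supports the drug in one result and speaks against it in the other.

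In a controlled trial, rescue in the comparator arm would offset part of this. Here the primary result is a within-patient change, so nothing separates the effect of the drug on polyp size from that of the operation. Rescue is plausible in this population, because entry requires failure of repeated systemic steroid courses or of earlier FESS.

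At stake is the meaning of the main result: a mean NPS reduction that is partly surgical would be reported as the effect of mepolizumab.

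**Working it through.** **1. The plan's own figure.** Inputs from Sample size calculation: d = 0.40, two-sided alpha 0.05, power 80%, paired t test, 20% drop-out. The noncentrality is 0.40 × √52 = 2.88 on 51 degrees of freedom. Exact power is 80.8% at n = 52 and 79.99% at n = 51, so 52 is the smallest adequate number. Enrolment is 52 / 0.80 = 65. Both stated figures reproduce, and this point does not change them.

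**2. What the documents do not give.** They state no rate of on-treatment FESS, no NPS fall after FESS, and no SD of the NPS change. All three are assumed below and shown over a range.

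**3. Model.** The drug has no effect. Change scores are normal with mean 0 and SD 1. A share f of patients is operated on, which lowers their 12-month NPS by k SDs of the change score.

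- Mean apparent improvement = f × k
- SD of the mixture = √(1 + f(1 − f)k²)
- Apparent standardised effect = f × k / √(1 + f(1 − f)k²)

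Example with f = 0.20, k = 2: mean 0.40; SD = √(1 + 0.16 × 4) = √1.64 = 1.281; effect = 0.40 / 1.281 = 0.31, against the planned 0.40.

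**4. Chance of a significant improvement.** Simulated, n = 52, 40,000 runs per cell, uncorrected two-sided paired t test at 0.05; nominal value in this direction 2.5%:

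| Share operated on | k = 1 SD | k = 2 SD | k = 3 SD |
|---|---|---|---|
| 5% | 5.3% | 8.9% | 12.2% |
| 10% | 9.8% | 21.6% | 33.3% |
| 15% | 16.5% | 39.9% | 58.4% |
| 20% | 25.6% | 60.2% | 79.9% |

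**5. With Bonferroni correction.** Six visits give 6 × 5 / 2 = 15 pairs. If all are corrected, the level per pair is 0.05 / 15 = 0.33% two-sided. For k = 2 SD, noncentral-t power at the apparent effects 0.092, 0.171, 0.244 and 0.312 is about 1%, 4%, 11% and 22% for 5%, 10%, 15% and 20% operated on. These are far smaller than in the table, but still above the nominal 0.33%.

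**6. Steroids.** No comparable calculation is possible. A course shortly before month 12 could lower NPS. A baseline NPS already suppressed by steroids, followed by less steroid use on mepolizumab, would work the other way.

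**The case against.** **A SAP could settle this.** It may exist, and rules for values after rescue are often placed there. But the protocol already fixes the primary endpoint and the method of analysis, and gives rescue a role only as a count. Followed as it stands, it produces the bias.

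**As-observed NPS is a legitimate real-life description.** Analysing outcomes regardless of rescue is a recognised choice, and reporting rescue counts alongside is informative. The protocol does not say that it makes this choice. It does say that it investigates sino-nasal efficacy of the drug, and without a comparator the as-observed change describes mepolizumab plus whatever rescue followed. That suits a sensitivity analysis better than the primary result.

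**The data are partly there.** This stands. On-treatment surgery is a collected variable and the visits are frequent, so a pre-surgery NPS should usually be available. A reader might infer from the Variables list that steroid use is captured only as regular medication. The secondary endpoint contradicts that: it cannot be reported without knowing who received systemic steroids. What is not specified is the dates.

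**The bias need not always favour the drug.** This also stands. A reader might infer that every rescue flatters mepolizumab. The documents do not support that for steroids: the introduction describes mepolizumab as reducing glucocorticoid use, and eligible patients may have had at least two courses in the past year, so the baseline itself may be suppressed. For surgery, some operated patients may stop the drug and have no month-12 value, and polyps may recur, since the study enrols patients whose earlier FESS failed.

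**Conclusion.** The point holds for surgery. As written, NPS after FESS enters the primary before-after comparison, and polyps removed surgically after drug failure count as improvement. For systemic steroids the distortion is possible, but its direction and size are uncertain.

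The size cannot be derived from the documents. The range of about 5% to 80%, against a nominal 2.5%, assumes no drug effect, 52 analysed patients, 5% to 20% operated on, a surgical effect of 1 to 3 SD still present at month 12, and an uncorrected paired t test. A reader might take a single cell of the table as this study's false-positive rate; it is not, because the surgery rate and effect are assumed and Bonferroni-corrected comparisons would give lower absolute figures. What does not depend on those inputs is the mechanism: a surgical fall still present at month 12 moves the primary result towards the drug, and more so as more failures are operated on.

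**What to change.** - **Primary analysis:** count NPS after on-treatment FESS as no improvement, for example by replacing it with the worse of the baseline value and the last value before surgery. Another prespecified failure rule would also close the gap.
- **Sensitivity, surgery:** report the as-observed analysis beside it.
- **Data:** ask centres for the date of each on-treatment sino-nasal operation and of each systemic steroid course. This should be set now, because part of the cohort is retrospective and details not requested may be hard to recover.
- **Sensitivity, steroids:** handle NPS after a systemic steroid course in the same way as NPS after FESS, as a sensitivity analysis only.

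The cost is one analysis rule and a few data fields. Sample size and patient care are unchanged. The reported mean improvement may be somewhat smaller; if few patients are operated on, it will hardly change.

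### The protocol does not say whether NPS is retrieved after mepolizumab is stopped, and its complete-visit analyses risk a 12-month estimate that favours patients who stayed on the drug

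*Protocol*

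**What the plan says.** - **Endpoints:** the primary endpoint is improvement in NPS "at 12 months after start of therapy". No condition of still being on treatment is attached.
- **Procedures, visits:** the schedule is introduced as usual care for patients receiving the drug, in whom "follow-up is continued with clinical re-evaluation every 3 months in the first year of treatment". For that reason centres are asked for the visits at 30 days and at 3, 6, 9 and 12 months, counted from the beginning of therapy.
- **Procedures, stopping:** centres must also report "any discontinuation of Mepolizumab due to adverse effects, intolerance to the drug, or related to its inefficacy". Sino-nasal surgery is recorded while the patient is on treatment. Nothing is said about NPS after the drug is stopped.
- **Sample size calculation:** "a sample size of 52 patients achieves 80% power to reject the null hypothesis of zero effect size when the population effect size is 0.40", based on a "two-tailed Student's t test for paired data". Then: "Anticipating a 20% drop-out rate, 65 patients should be enrolled to obtain the final sample size of 52 subjects". Drop-out is not defined.
- **Statistical Analysis:** NPS and the other scores over time are tested by repeated-measures ANOVA or Friedman's test. In addition, "Potential predictors of clinical response at each time point will instead be assessed by univariable and multivariable logistic regression models", using scores from the visit just before.

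**The concern.** The endpoint is counted from the first dose, but the data collection that feeds it is explained by the care of patients still on the drug. A centre abstracting charts could reasonably end the record when mepolizumab is stopped, and no sentence tells it to go on. The named analyses would then remove that patient altogether.

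The protocol expects some patients to stop because the drug does not work for them, so this loss would be related to the outcome. In a single-arm before-after study no comparator shares it. The stated interest is effectiveness in real life, which concerns everyone who started. An estimate from patients who persisted answers a narrower question, and probably a more favourable one.

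**Working it through.** **1. The plan's own figures.** Inputs from Sample size calculation: standardised change d = 0.40, two-sided alpha 0.05, power 80%, paired t test, 20% drop-out.

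- Noncentrality for n = 52: 0.40 × √52 = 2.88, with 51 degrees of freedom. Exact power is 80.8%. With n = 51 it is 79.99%, so 52 is the smallest n that reaches 80%.
- Enrolment: 52 / (1 − 0.20) = 65. The expected loss is 65 − 52 = 13.

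Both figures reproduce. The calculation is not at fault.

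**2. The path of a patient who stops.** Take, as an example, a patient who stops for inefficacy at month 4 and whose later NPS is not retrieved. Baseline, 30 days and 3 months are available; 6, 9 and 12 months are not.

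- Repeated-measures ANOVA and Friedman's test, in standard form, need every visit, so the patient is omitted.
- A paired comparison of baseline with month 12 also omits the patient.
- The 6-month response model has no outcome for this patient. The 9- and 12-month models have neither the outcome nor the score from the preceding visit.

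A clear non-responder would therefore be missing from the primary estimate and from three response models.

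**3. Illustration of size.** The protocol gives no NPS results by treatment status, so these inputs are assumptions. Let a share p stop and be excluded, let m be the mean change in stayers, and let s be the mean change in those who stop.

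Mean over all starters = (1 − p) × m + p × s

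Overstatement ratio = m / [(1 − p) × m + p × s]

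When s = 0 the ratio is 1 / (1 − p), whatever the effect size:

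- p = 0.20: 1 / 0.80 = 1.25, or 25% too high.
- p = 0.10: 1 / 0.90 = 1.11, or 11% too high.

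With p = 0.20, m = 0.40 and other values of s (in SD units):

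| Change in those who stop | Mean, all starters | Ratio |
|---|---|---|
| 0.40 | 0.32 + 0.08 = 0.40 | 1.00 |
| 0.20 | 0.32 + 0.04 = 0.36 | 1.11 |
| 0.00 | 0.32 | 1.25 |
| −0.20 | 0.32 − 0.04 = 0.28 | 1.43 |

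The first row matters: if those who stop did as well as those who stayed, there is no bias in the mean.

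**4. Consequence for power.** Suppose 0.40 describes stayers, those who stop do not change, and the SD within each group is 1. The SD over all starters is √(1 + 0.80 × 0.20 × 0.40²) = 1.013, so d = 0.32 / 1.013 = 0.316, and power with all 65 analysed is 70.9%. If 0.40 holds for all starters, power with 65 is 88.8%. The protocol does not say to which group 0.40 refers.

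**The case against.** The strongest reply is that the protocol nowhere removes these patients.

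- The requested visits and the endpoint are both counted from the start of therapy, and discontinuation data are requested in addition to those visits, not in their place. The reference to the first year of treatment describes usual practice and explains the choice of time points. **This stands.** It means the text is silent on visits after stopping; it does not exclude them.
- A reader might infer from the 52-of-65 sentence that 13 patients are to be left out of the analysis. **The documents do not support that.** The sentence is an ordinary inflation. Drop-out is not equated with stopping mepolizumab and could equally mean transfer, a missed visit or an unrecorded NPS.
- Analysis sets and missing-data rules commonly belong to a SAP, and one may exist. **This stands in part.** A SAP can define the set, but it cannot analyse a month-12 NPS that centres did not know to retrieve, and this protocol itself names methods that need complete visits.
- Patients who stop for adverse effects or intolerance may have had polyp reduction, so upward bias is not certain. **This stands**, and it is why the figures are illustrations.
- If visits end when the drug is stopped, new wording will not create an NPS. **This stands for those patients.** The instruction recovers only what routine care records.

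**Conclusion.** The concern holds as a gap in data collection combined with complete-visit methods. The protocol does not say whether NPS is retrieved after mepolizumab is stopped. Its treatment-based account of follow-up, its allowance for 20% loss and its named tests together make it likely that patients who stop for inefficacy drop out of the 12-month estimate and the later response models. With no comparator, improvement among all who started may be overstated.

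Two stronger readings should be avoided: that the protocol excludes patients who stop, and that the result will be 25% too high. No exclusion rule is written. The 25% (or 11% at 10% stopping) assumes that every excluded patient stopped the drug and had no NPS change. The true size cannot be derived from the document. The point merits a change because the change is cheap.

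**What to change.** **Procedures.** State that stopping mepolizumab is not drop-out. Ask centres to retrieve any routine ENT visit at 3, 6, 9 and 12 months from first dose whatever the treatment status, and to record at each visit whether the drug is still taken and whether a new biologic has been started.

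**Statistical Analysis.**

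- Analyse NPS in all patients who started, with a method that keeps incomplete series, such as a mixed model, in place of complete-visit ANOVA or Friedman's test.
- Count patients who stopped for inefficacy as non-responders in the later response models.
- Add a sensitivity analysis that assigns zero NPS change to inefficacy stoppers with no later NPS. It is needed because a mixed model, under its usual missing-at-random assumption, projects their month 12 from patients who stayed on the drug. Zero change is one reasonable choice among several, so it should not be the primary rule.
- Report the on-treatment result as supportive.

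**Cost.** A few sentences and two case-report-form fields; no new procedure, since only routine visits are used. The reported improvement may be smaller, and some patients who stop will still have no NPS in the chart.
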